#### **Protocol**

Study Title: Integrative Medicine for Hypermobility Spectrum Disorder (HSD) and Ehlers-Danlos (EDS) syndromes: A mixed-methods feasibility study (IMforHSDandEDS)

PI: [name]

IRB #: DH10320/PRAF

Approval Date: 03.03.21

Version: 3.0

used for pain that the participant is taking will also be documented, but no changes in medications will be required by the study. Current self-reported weight will also be documented.

#### **E.4.6.1 Food Plan Satisfaction Survey**

We will distribute food plan satisfaction surveys via REDCap to be completed by the participant prior to Visit # 3. (See Appendix 2Fii)

#### **E.4.7 Check-in #2 (6 weeks)**

Participants will receive a phone call or e-mail from the student researcher that will answer any questions, provide nutritional and psychosocial support, and offer solutions to any dietary challenges. The goal is to provide support with dietary adherence. This will occur 2 weeks after Visit # 2 and will be set up in advance at a time that works for the participant. If the participant is not available, we will send a check-in email and answer any questions, provide nutritional and psychosocial support, and offer solutions to any dietary challenges by email, if requested. The Nutrition counseling script contains suggestions for a general healthy eating pattern but is not a part of food plan adherence. (See Appendix 3B)

Participants will be assessed for any adverse events with the following question, "Are you experiencing any new symptoms or side-effects that you may have noticed?" (See Appendix 3B)

#### **E.4.8 Visit # 3: Follow-up (9 weeks)**

During the final virtual visit, the student researcher will collect VAS pain measurements, patient assessment of care for chronic conditions (PACIC+), PROMIS-29 health-related quality of life scores and will assess participants for any adverse events using the NUNM standardized multi-system questionnaire.

The Clinical Investigator will discuss the social and familial support of the patient, provide psychosocial support, and address any concerns with the anti-inflammatory food plan. The CI will also assess the patient's current self-management strategies and provide suggestions for any adjustments to general behavioral and psychosocial support recommendations. Any current medications or supplements being used for pain that the participant is taking will also be documented, but no changes in medications will be required by the study. Current self-reported weight will also be documented.

At the final visit, patients will be encouraged to continue to eat a healthy diet but will be reminded that the study is complete and that they may alter their diet in whatever way they wish.

### **E.5 Intervention**

#### *9-week integrative medicine intervention*

Enrolled participants will take part in a 9-week program that includes a novel integrative medicine intervention that is focused on patient-centered care. The patient will establish a therapeutic

#### **Protocol**

Study Title: Integrative Medicine for Hypermobility Spectrum Disorder (HSD) and Ehlers-Danlos (EDS) syndromes: A mixed-methods feasibility study (IMforHSDandEDS)

PI: [name]

IRB #: DH10320/PRAF

Approval Date: 03.03.21

Version: 3.0

relationship with a holistic healthcare provider team consisting of a medical doctor and a student researcher to support comprehensive care. Participants will attend a total of 3 visits with a medical doctor over the 9-week integrative medicine intervention.

The Clinical Investigator has created a 9-week program that is composed of a prescribed anti-inflammatory (Mediterranean) food plan as well as general behavioral and psychosocial support. During the 3 consultations with the participant, the CI will: 1) Capture a complete and detailed medical history and background, 2) Discuss familial and social support, 3) Provide psychosocial support, 4) Assess the patient's current self-management strategies for self-care, and 5) Assess the patient's current self-management strategies for mental health. Study personnel will also follow provide psychosocial and nutritional support to address any additional concerns and promote adherence to the food plan.

#### *Prescribing an anti-inflammatory food plan and assessment of current diet*

The Clinical Investigator will prescribe an anti-inflammatory food plan that consists of a high intake of fruits and vegetables (4-5 serving of each per day). The specific dietary requirements for adherence to the anti-inflammatory food plan incorporated in this 9-week integrative medicine intervention will include macronutrient levels similar to those of a Mediterranean diet, which breaks down to 40-50% carbohydrates, 15-20% protein, and 35-40 % fat. Such a diet is high in fiber, micronutrients, healthy fats, and antioxidants that may provide health benefits by reducing inflammation. The Clinical Investigator will present the macronutrient requirements, assess the current diet of the participant, and suggest modifications that will cause their diet to conform to study guidelines, such as reducing sugar as well as processed and fast foods. They will discuss removing trans fats and hydrogenated oils and replacing them with cold-pressed and unrefined oils. For simplicity and accuracy, participants will be advised to follow a "Mediterranean-style eating pattern," which is very searchable among recipe databases and websites, and more specific than the term "anti-inflammatory."

Participants will be provided an anti-inflammatory food plan that includes recipes, a guide for adding and reducing certain foods, and obtaining targeted macronutrient levels (see above) if modification of their current diet seems infeasible, or if they so desire. The student researcher will assess the cooking skills of participants and provide resources, as needed (i.e. YouTube channels, websites). They will discuss meal-planning, meal-prepping, and making a grocery list on a budget as needed. Additionally, participants will be contacted twice via phone or email by the student researcher to provide nutritional and psychosocial support, answer any questions, and facilitate adherence.

#### *Capturing a complete and detailed medical history and background*

The Clinical Investigator will comprehensively intake the patient's full medical history and listen to their entire background. Because HSD and ESD can be a frustrating and invalidating prognosis, extreme sensitivity and empathy will be used to build trust and develop a therapeutic relationship with the participants.

#### **Protocol**

Study Title: Integrative Medicine for Hypermobility Spectrum Disorder (HSD) and Ehlers-Danlos (EDS) syndromes: A mixed-methods feasibility study (IMforHSDandEDS)

PI: [name]

IRB #: DH10320/PRAF

Approval Date: 03.03.21

Version: 3.0

Patients suffering from these conditions report that the limitations they receive within the healthcare system often involve a lack of awareness of HSD or EDS from providers, and hold similar perceptions that they have been ignored, belittled, or considered to have hypochondria when they do seek advice. The Clinical Investigator will approach the participants by validating their experience with an emphasis on reinforcing the feeling that participants are and being heard, believed, and listed to attentively.

#### Discussing familial and social support

The Clinical Investigator will assess what and intrapersonal support the participants have, which can help influence long-term health changes. Motivational interviewing will be utilized and “include *engaging* with patients to help build rapport, *focusing* patients on the changes they want to make while offering advice and support, *evoking* the tools, and desires they possess within them to effect change, and *planning* to implement the goals and next steps patients identified through the encounter.”

The Clinical Investigator will assess the general support that the participants have in their home, or in the community where they live, to make dietary and lifestyle changes. This will involve discussing any barriers they have, such as grocery store and transportation access, and practical needs like having a kitchen, tools to cook, or time to prepare fresh food. Potential solutions to these barriers like community food pantries and cooking classes will be recommended depending on the location of the participant. The CI will also assess the social network of the participant for supportive relationships that are necessary to create healthy behavior changes. Recommendations will be made in accordance with the needs of the participant and may include referrals to the Portland area EDS support group, or Oregon Area Ehlers-Danlos Society if they require more assistance.

#### Providing psychosocial support

Psychosocial support will be provided by both the Clinical Investigator, the student researcher, and *MyFitnessPal* throughout the 9-week program. Participants will receive behavioral, lifestyle, and dietary counseling all through a total of 3 office visits with the medical doctor, and 2 phone calls or e-mail check-in correspondences with the student researcher.

The student researcher has personal experience with both hEDS and Postural Tachycardia Syndrome (POTS), and similar to another EDS study, this will be disclosed to participants at the beginning of the interview in an effort to mitigate the power imbalance that often accompanies research. This may also help “instill greater confidence in participants” to share their experiences with a researcher and EDS individual who is also in their “in-group.” It will also be “emphasized that it [is] their stories that matter” for the purpose of the study.

#### MyFitnessPal

#### **Protocol**

Study Title: Integrative Medicine for Hypermobility Spectrum Disorder (HSD) and Ehlers-Danlos (EDS) syndromes: A mixed-methods feasibility study (IMforHSDandEDS)

PI: [name]

IRB #: DH10320/PRAF

Approval Date: 03.03.21

Version: 3.0

*MyFitnessPal*, a food tracker available on both Apple and Android for mobile devices, as well as both Windows and Mac computer platforms, will be used to collect estimated daily dietary intake for participants. *MyFitnessPal* has a database of nutritional information for over 11 million foods that will allow participants to capture their general diet by manually adding individual ingredients, barcode scanning, or finding whole meals. In a comparison of micronutrients and calories between diet-tracking apps and the USDA database, *MyFitnessPal* was shown to have the best coding accuracy. Self-reported data, however, may be subject to inaccuracies. When foods are entered into the *Diary* feature located in the app, the *Nutrient Dashboard* displays daily calories, as well as macronutrient proportions, broken down into carbohydrates, fats, and protein.

Participants will be encouraged to track their daily diet to the best of their ability, and for weeks that there is missing data, a threshold of no less than 3 days of tracking (including breakfast, lunch, dinner, and snacks) per week for the 9-week study duration will be considered adherent and averaged appropriately. Individuals with previous disordered eating patterns, or discomfort with food tracking, will be able to opt-out; however, they will still be shown how to use *MyFitnessPal* to analyze dietary composition for adherence. A 1-week lead-in prior to introducing the food plan will be utilized to provide a baseline record of the participant's general diet. *MyFitnessPal* data will allow us to track general adherence to dietary changes, the overall quality of the participant's diet, and average macronutrient proportions. By measuring the participant's reported macronutrient percentage scores and comparing them with the prescribed food plan, we will be able to calculate an adherence score.

*MyFitnessPal* usage has been shown to have positive results for behavioral and health changes, and for meeting nutrition-related goals, and was found to be associated with higher levels of reported self-efficacy among users that reported more frequent use. In a systematic review of dietary mobile app use and chronic diseases, it was concluded they may be effective self-monitoring tools and were shown to have positive effects on measured nutritional outcomes. Other small studies have shown that wearable technology may provide additional psychosocial support for dietary interventions and behavioral change. Most health and fitness apps have also been shown to incorporate health behavior theory, which is essential for behavioral change. In a focused review of smartphone diet-tracking apps, *MyFitnessPal* was shown to have better usability when compared to other apps; however, one disadvantage that the review cited for all diet-tracking apps was that users lack the ability to track their emotions.

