## Protocol

Study Title: Integrative Medicine for Hypermobility Spectrum Disorder (HSD) and Ehlers-Danlos (EDS) syndromes: A mixed-methods feasibility study (IMforHSDandEDS)

PI: [name]

IRB #: DH10320/PRAF

Approval Date: 03.03.21

Version: 3.0

**B.3 Tertiary Aim:** To examine the effect of a 9-week integrative medicine intervention on overall perceived pain and quality of life in patients with Hypermobility Spectrum Disorder (HSD) or Ehlers-Danlos syndromes (EDS).

- Outcome Measures 3: Participants will complete a Visual Analog Scale for Pain (VAS Pain) and a 29-Item profile HRQoL Survey (PROMIS-29) at baseline, 5, and 9 weeks.

In order to better understand the needs of the patient population, we will also address the following exploratory aims, as far as we are able. These aims can be considered to be independent of the effects of treatment.

**B.4 Exploratory Aim 1:** To evaluate any associations between symptom severity, perceived pain, quality of life, and diet among patients with Hypermobility Spectrum Disorder (HSD) or Ehlers-Danlos syndromes (EDS).

- Participants will be given a 1-week lead-in to establish baseline food patterns before starting the prescribed food plan. Associations of dietary composition, patient-reported symptoms, as well as overall perceived pain and quality of life scores will be examined, both cross-sectionally at intake and longitudinally over the 9 weeks of the intervention.

**B.5 Exploratory Aim 2:** To assess the experiences of chronic illness care and living with chronic illness among patients with Hypermobility Spectrum Disorder (HSD) or Ehlers-Danlos syndromes (EDS).

- Outcome Measure 5: Participants will complete a 26-item survey, Patient Assessment of Chronic Illness Care (PACIC+), that evaluates areas of patient self-management within the chronic care model of healthcare. The PACIC+ ascertains attitudes regarding patient-centered care, living with chronic illness, and chronic illness care; it will be completed by participants at baseline and 9 weeks.

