### **E.4 Participant and Procedure Schedule**

#### **E.4.1 Overview**

The study is comprised of 1 in-person screening, 2 follow-up visits, and 2 telephone or email check-in correspondences for additional support. The in-person screening and 2 virtual follow-up visits will take place at the Healthy Living Community clinic. Virtual follow-up study visits will take place via the Zoom video platform utilized by ChARM TeleHealth, a web-based and HIPAA compliant server maintained by the Healthy Living Community clinic and will occur at 5- and 9-weeks post-enrollment.

During the in-office screening, participants will have their joint mobility measured in accordance with the Brighton Scoring System to confirm that they meet the diagnostic criteria for Hypermobility Spectrum Disorder. Participants who are diagnosed using the Brighton criteria and meet other eligibility criteria will then be asked to provide informed consent (E.4.3) and enrolled in the study if willing. The Clinical Investigator will capture a complete and detailed medical history of enrolled participants, discuss family and social support, as well as prescribe a food plan. The CI will also assess the patient's current self-management strategies and provide general behavioral and psychosocial support. During the 2 follow-up visits, the Clinical Investigator will revisit these self-management strategies. As scheduling visits may be difficult at precisely 5 and 9 weeks, we will leave some flexibility for these points in time to accommodate the schedules of the Clinical investigator, the student researcher, and the participants.

At 2 and 6 weeks, the participants will be contacted by the student researcher to answer any questions, provide nutritional and psychosocial support, monitor for any adverse events, and offer solutions to any dietary challenges. Participants will also be assessed at all study visits for any adverse events.

Participants will be asked to complete pain (VAS), and health-related quality of life (PROMIS-29) instruments at baseline, 5, and 9 weeks. Adherence to the dietary recommendations, as well as the feasibility of food tracking will be obtained using *MyFitnessPal*, a food tracker app throughout the 9 weeks. A food plan satisfaction survey will be collected at 5 and 9 weeks. Participants will fill out the

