#### **Protocol**

Study Title: Integrative Medicine for Hypermobility Spectrum Disorder (HSD) and Ehlers-Danlos (EDS) syndromes: A mixed-methods feasibility study (IMforHSDandEDS)

PI: [name]

IRB #: DH10320/PRAF

Approval Date: 03.03.21

Version: 3.0

calculate the daily caloric needs for each patient using the estimated energy requirements (EER) formula for each patient that takes into consideration their current physical activity level (i.e. sedentary or active), weight, and age. The CI will request consent to obtain the medical records of the participant.

The Clinical Investigator will do a thorough review of the patient's full medical history and listen to their entire background. They will discuss the social and familial support of the patient, assess their general diet, provide psychosocial support, and prescribe an anti-inflammatory food plan. The Clinical Investigator will also assess the patient's current self-management strategies and provide general behavioral and psychosocial support. Any current medications or supplements being used for pain that the participant is taking will also be documented, but no changes in medications will be required by the study. Participants will be given portal access to their electronic health records through ChARM Patient Portal for the use only of this study.

The student researcher will assist participants with logging into REDCap and collecting baseline pain (VAS), health-related quality of life (PROMIS-29) and patient assessment of care for chronic conditions (PACIC+) surveys. A baseline adverse events questionnaire will be obtained using the NUNM standardized multi-system survey for each participant, to document any current health conditions that may not be listed in the medical record. Participant demographic information will be collected, including age, sex, and gender

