The student researcher will provide flyers with advice and guidelines for following a meal plan that follows an anti-inflammatory eating pattern, including recommendations for meal planning and strategies for adding and reducing certain foods (See Appendices Gi through Giv). The macronutrient breakdown that will be recommended for the patients will be 40- 50 % carbohydrate, 15- 20 % protein, and 35- 40 % fat, which is aligned with the Mediterranean-style eating pattern and has been shown to be anti-inflammatory. Participants will be provided a food plan that is in accordance with their current average dietary consumption of either 1800 or 2200 calories. (See Appendices 2Gi through 2Giv) Participants will also be given a list of resources for online and local Mediterranean-style eating patterns to simplify their research options. (See Appendix 2Gvi)

The student researcher will assist participants with downloading *MyFitnessPal* so that their estimated daily dietary intake can be captured. Participants will be assigned a *MyFitnessPal* username using an unidentifiable study number that will be recorded by the student researcher in a secure location, and the account will only be used for study purposes. Participants will be instructed that no identifiable health data related to the study will be shared on the *MyFitnessPal* app. The student researcher will also review the Sharing & Privacy settings in the *MyFitnessPal* app with participants to ensure that the privacy is protected as much as possible.

They will also provide a handout for how to use the app or website (See Appendix 2Gv). Participants will be given an opportunity to practice using the app with support from the study coordinator. Participants will be encouraged to track their diet daily to the best of their ability and will be able to opt-out of tracking if they express concerns. Using the Friends feature on the app, participants will be able to share

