### **Protocol**

Study Title: Integrative Medicine for Hypermobility Spectrum Disorder (HSD) and Ehlers-Danlos (EDS) syndromes: A mixed-methods feasibility study (IMforHSDandEDS)

PI: [name]

IRB #: DH10320/PRAF

Approval Date: 03.03.21

Version: 3.0

their daily food tracking with the student researcher, and the data will be collected at 5 and 9 weeks. Participants will be given a 1-week lead-in period so that they can adjust to tracking their dietary intake before starting the food plan and will be instructed to contact the student researcher with any questions.

In the event that the baseline visit is conducted virtually, all procedures will be the same, except that the participant will provide medical documentation of a Beighton score of 4 or more, in lieu of a Beighton measurement being obtained at the visit. We will require informed consent prior to capturing this documentation. The participant will be asked to report their own height and weight. All other data will be captured electronically. Any participant who completes the baseline visit remotely will be invited to complete the Week 5 visit in person, if possible; if the Week 5 visit is completed in person, then weight, height, and Beighton score will be confirmed at that visit.

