### **Protocol**

Study Title: Integrative Medicine for Hypermobility Spectrum Disorder (HSD) and Ehlers-Danlos (EDS) syndromes: A mixed-methods feasibility study (IMforHSDandEDS)

PI: [name]

IRB #: DH10320/PRAF

Approval Date: 03.03.21

Version: 3.0

burden, support needed, and any barriers that are encountered with the recommended dietary modifications.

- Because these measures are reported as open responses, they will be thematically summarized for representative quotes, at each time point measured.

Adherence with dietary tracking will be assessed by:

- Percentage of total days on which dietary intake was documented. Self-reporting of daily dietary intake on at least 50% of total days will be considered adherent.
- Number of weeks on which intake was self-reported at least 3 days.

For Specific Aim 3,

We will test whether the integrative medicine education intervention reduced pain and improved health-related quality of life in patients with HSD or EDS. VAS pain scores and PROMIS-29 domain scores will be summarized across participants and time points as mean (SD).

Analysis of pain and HRQoL outcomes for Aim 2 will use paired t-tests to assess mean changes unless investigation of distributions indicates a need for nonparametric testing, in which case changes will be analyzed using Wilcoxon signed-rank tests.

For Exploratory Aim 1,

Any associations between pain, HRQoL, and diet will be assessed both cross-sectionally and longitudinally over the course of treatment. Cross-sectional associations of VAS pain score, PROMIS-29 domain scores, and dietary composition measures will be analyzed using Pearson correlations (or Spearman correlations for badly non-normal data). To assess associations of longitudinal changes, we will compute changes in each measure both from baseline to 5 weeks, and from baseline to 9 weeks, and we will similarly evaluate correlations between the changes over each time period.

Cross-sectional correlations assess the association of participants' ordinary diet with pain and health-related quality of life, while correlations of changes assess the association of dietary changes, in response to the treatment recommendations, with changes in pain and HRQoL over the same time frame.

We will also assess associations between age, race, sex, baseline symptoms, and changes in outcomes at follow-up, using Pearson correlations and independent t-tests, as appropriate.

For Exploratory Aim 2,

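### The lead-in week is described as a diet record made before the food plan is introduced, but the plan, targets and counselling are given at Visit 1, so it cannot safely be read as ordinary diet in Exploratory Aim 1

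*Combined protocol and SAP*

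**What the plan says.** The protocol describes the lead-in week in three ways.

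- **As a record made before the plan is introduced.** E.5, under MyFitnessPal: "A 1-week lead-in prior to introducing the food plan will be utilized to provide a baseline record" of the participant's general diet.
- **As a record made before the plan is started.** B.4 (Exploratory Aim 1): "Participants will be given a 1-week lead-in to establish baseline food patterns before starting the prescribed food plan". The Abstract gives the same purpose, also in terms of starting the plan.
- **As practice with the app.** E.4.4 says the week is there "so that they can adjust to tracking their dietary intake before starting the food plan".

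The procedures put the dietary intervention at Visit 1. E.4.1 has the investigator "discuss family and social support, as well as prescribe a food plan" once the participant is enrolled. E.4.4 has the investigator "assess their general diet, provide psychosocial support, and prescribe an anti-inflammatory food plan", and adds: "The student researcher will provide flyers with advice and guidelines for following a meal plan". At the same visit participants receive the recommended macronutrient breakdown, a calorie-matched food plan and a resource list.

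E.9 says that the cross-sectional correlations under Exploratory Aim 1 assess the association of participants' "ordinary diet with pain and health-related quality of life". It computes dietary change from baseline to week 5 and to week 9.

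**The concern.** A baseline diet record is useful for Exploratory Aim 1 only if it reflects what people ate before the study tried to change it. Here participants would log the baseline week with the targets, recipes and advice already in hand.

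Two analyses depend on that week. The cross-sectional correlations would be reported as concerning ordinary diet, although they came from a week recorded after counselling. The change scores would start from a point the intervention may already have moved. The pain and quality-of-life baselines are taken at Visit 1, before the lead-in. Any early dietary shift would then be missing from the dietary change, while any effect it had on symptoms would count in the symptom change.

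**Working it through.** The plan states no figure to reproduce. The check is of the order of events, followed by a short illustration.

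**Order of events**

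1. *Visit 1 (E.4.1, E.4.4).* The plan is prescribed, the handouts and macronutrient breakdown are given, and the app is set up. The E.5 subsection on prescribing the plan adds that the investigator presents the macronutrient requirements and suggests changes to bring the diet into line with them.
2. *Lead-in week (E.4.4).* One week of tracking follows Visit 1.
3. *Next contact (E.4.5).* A check-in by phone or e-mail two weeks after Visit 1. The investigator's next visit is at week 5 (E.4.6).

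No contact is scheduled at the end of the lead-in, so there is no later point at which the plan could first be introduced. Steps 1 and 2 cannot be squared with the E.5 statement that the lead-in comes first.

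**Which record is the baseline**

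E.9 does not mention the lead-in. The link comes from B.4, which makes the lead-in the source of baseline food patterns and plans associations at intake and over follow-up. The investigator's diet review at Visit 1 is not listed in E.6 as a measure of dietary composition. The lead-in log is therefore the only recorded dietary baseline the protocol describes.

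**What a shift would do**

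Let D be the true dietary change from ordinary diet to follow-up, and f the share of it already made during the lead-in.

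Measured change = (1 − f) × D

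| f (assumed) | Measured change as a share of D |
|---|---|
| 0 | 1 − 0 = 100% |
| 0.25 | 1 − 0.25 = 75% |
| 0.50 | 1 − 0.50 = 50% |

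The documents give no value for f. A negative f (participants moving away from the plan before a known start date) would make measured change exceed D.

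**What it would do to the correlations**

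If f is the same for everyone and below 1, each change score is multiplied by the same positive constant. Pearson and Spearman correlations with symptom change are then unaltered. They move only if f differs between participants. That is plausible with individual counselling, but the documents do not show it.

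**Scope**

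- Recruitment and retention do not use the lead-in.
- Dietary adherence is scored against fixed macronutrient ranges (E.6, E.9), not against baseline.
- VAS pain and PROMIS-29 baselines are collected at Visit 1.

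Only Exploratory Aim 1 depends on the lead-in diet as a baseline.

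**The case against.** The strongest reply is that the protocol is coherent apart from one verb. The Abstract, B.4 and E.4.4 all speak of *starting* the plan after the lead-in, so participants receive it at Visit 1 and begin it a week later. On that reading only E.5, with *introducing*, is wrong. This stands in part: participants are told of a later start, and nothing shows that they change their diet early. But a later start delays adherence, not exposure to the targets. The app also displays macronutrient proportions to the user, and E.5 itself cites evidence that using it changes behaviour.

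A reader might go further and infer that the baseline has been shown to be contaminated, that dietary change will be understated by a known amount, or that its correlation with pain change will be weakened. The documents support none of these. They show exposure only. Understatement requires movement toward the plan, and a changed correlation requires shifts that differ between participants.

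Figure 2 and the participant handouts are not available in the text reviewed. An instruction to keep the usual diet during the lead-in could be there. That would reduce the risk of a shift, but it would not remove the conflict over when the plan is introduced.

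Finally, the aim is exploratory, offered as far as the team is able, and based on at most 20 participants without a control group. That is a fair argument for low priority.

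**Conclusion.** The inconsistency is real. The procedures do not deliver the pre-introduction diet record that E.5 promises, and E.9's description of the cross-sectional data as ordinary diet does not follow from them. The lead-in record also cannot be taken as an unexposed baseline for dietary change.

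No size or direction of bias can be stated; the percentages above are assumptions. The conclusion rests on two readings: that the lead-in log supplies the baseline diet data, as B.4 indicates, and that Visit 1 runs as E.4.4 describes. A reader might infer that the feasibility results are compromised. They are not: recruitment, retention and adherence scoring do not use the lead-in as a baseline, and the symptom baselines are taken before it. Low priority, but worth correcting because it changes how Exploratory Aim 1 can be reported.

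**What to change.** Reconcile the Abstract, B.4, the MyFitnessPal part of E.5 and E.9 with E.4.1, E.4.4 and the E.5 text on prescribing the plan. There are two ways, and the choice is the sponsor's.

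- **Reorder the procedures to match E.5.** Lead-in tracking would come before the targets, dietary counselling and handouts. The cost is more than a delayed e-mail. The investigator's in-person dietary counselling would have to move as well, and no investigator contact is now scheduled between Visit 1 and week 5. Some reactivity to the app could remain.
- **Keep the procedures and correct the description.** Call the lead-in a post-counselling run-in and remove from E.5 the statement that it comes before the plan is introduced. Qualify the Abstract and B.4 to match. In E.9, stop interpreting the cross-sectional correlations as those of ordinary diet, and state that change measured from the lead-in may understate dietary change. This costs only wording and a less favourable interpretation, and changes nothing participants receive.
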